8.6 Pregnancy

If a participant inadvertently becomes pregnant while on treatment with study agent, the participant will immediately be discontinued from the study therapy, and followed for safety and efficacy evaluation as possible. The site will contact the participant at least monthly and document the participant's status until the pregnancy has been completed or terminated. The pregnancy will be recorded on the case report form (CRF) and reported by the Investigator to the Institutional Review Board (IRB).

Any pregnancy that occurs during a clinical study with an investigational medicinal product must be reported within 24 hours of learning of its occurrence. The pregnancy should be followed to determine outcome, including spontaneous or voluntary termination, details of the birth, and the presence or absence of any birth defects, congenital abnormalities, and/or any pregnancy- or childbirth-related and/or newborn complications. The pregnancy should be recorded on a case report form (CRF) and reported by the Investigator to Secura Bio. Pregnancy follow-up should be reported using the Pregnancy Follow up Form. Any SAE experienced during pregnancy must be reported.

The Investigator should counsel any pregnant subject and discuss the risks of continuing with the pregnancy and the possible effects on the fetus. Additionally, the pregnant woman should be referred to an obstetrician/gynecologist experienced in reproductive toxicity for further evaluation and counseling. Monitoring of the subject should continue at least until delivery or until the pregnancy has terminated.

If, while on study treatment a male study participant's sexual partner becomes pregnant by said study participant, the pregnancy and pregnancy outcomes must also be reported as described above. Consent to report information regarding the pregnancy should be obtained from the pregnant individual.

8.7 Overdose

An overdose is defined as the accidental or intentional administration of any dose of a product that is considered both excessive and medically important. All occurrences of overdose must be reported as an SAE.

8.8 Potential Drug Induced Liver Injury

Whenever possible, timely confirmation of initial liver-related laboratory abnormalities should occur prior to the reporting of a potential drug-induced liver injury (DILI) event. All occurrences of potential DILIs, meeting the defined criteria below, must be reported as SAEs (see Section 8.1.1 for reporting details).

Potential drug induced liver injury is defined as:

- AT (ALT or AST) elevation > 3 times upper limit of normal (ULN) AND
- Total bilirubin > 2 times ULN, without initial findings of cholestasis (elevated serum alkaline phosphatase), AND
- No other immediately apparent possible causes of AT elevation and hyperbilirubinemia, including, but not limited to, viral hepatitis, pre-existing chronic or acute liver disease, or the administration of other drug(s) known to be hepatotoxic.

9.0 Safety Information: Sponsor and Investigator Responsibilities

9.1 Review of Safety Information: Sponsor Responsibilities

The sponsor must promptly review all information relevant to the safety of the drug obtained or otherwise received by the sponsor from foreign or domestic sources, including information derived from any clinical or epidemiological investigations, animal or in vitro studies, reports in the scientific literature, and unpublished scientific papers, as well as reports from domestic and foreign regulatory authorities and reports of domestic and foreign commercial marketing experience.

Note : The requirements of the manufacturer for the reporting of suspected adverse drug reactions to the FDA differ from the requirements of the sponsor Investigators (see below and Investigator Responsibilities on the O3IS website) for the reporting of adverse events. Sponsor-investigators of IND applications are subject to compliance with both the adverse reaction reporting requirements of the Sponsor and the adverse event reporting requirements of the Investigator.

9.2 IND Safety Reports

The sponsor must notify FDA and all participating investigators (i.e., all investigators to whom the sponsor is providing drug under its INDs or under any investigator's IND) in an IND safety report of potential serious risks, from clinical trials or any other source, as soon as possible, but in no case later than 15 calendar days after the sponsor determines that the information qualifies for reporting under Sections 9.2.1 to 9.2.4 below. In each IND safety report, the sponsor must identify all IND

safety reports previously submitted to FDA concerning a similar suspected adverse reaction, and must analyze the significance of the suspected adverse reaction in light of previous, similar reports or any other relevant information.

9.2.1 Serious and unexpected suspected adverse reaction

The sponsor must report any suspected adverse reaction that is both serious and unexpected. The sponsor must report an adverse event as a suspected adverse reaction only if there is evidence to suggest a causal relationship between the drug and the adverse event, such as:

- A single occurrence of an event that is uncommon and known to be strongly associated with drug exposure (e.g., angioedema, hepatic injury, Stevens-Johnson Syndrome);
- One or more occurrences of an event that is not commonly associated with drug exposure, but is otherwise uncommon in the population exposed to the drug (e.g., tendon rupture);
- An aggregate analysis of specific events observed in a clinical trial (such as known consequences of the underlying disease or condition under investigation or other events that commonly occur in the study population independent of drug therapy) that indicates those events occur more frequently in the drug treatment group than in a concurrent or historical control group.
-

9.2.2 Findings from other studies

The sponsor must report any findings from epidemiological studies, pooled analysis of multiple studies, or clinical studies (other than those reported under section 1.5.1), whether or not conducted under an IND, and whether or not conducted by the sponsor, that suggest a significant risk in humans exposed to the drug. Ordinarily, such a finding would result in a safety-related change in the protocol, informed consent, investigator brochure (excluding routine updates of these documents), or other aspects of the overall conduct of the clinical investigation.

9.2.3 Findings from animal or in vitro testing

The sponsor must report any findings from animal or in vitro testing, whether or not conducted by the sponsor, that suggest a significant risk in humans exposed to the drug, such as reports of mutagenicity, teratogenicity, or carcinogenicity, or reports of significant organ toxicity at or near the expected human exposure. Ordinarily, any such findings would result in a safety-related change in the protocol, informed consent, investigator brochure (excluding routine updates of these documents), or other aspects of the overall conduct of the clinical investigation.

9.2.4 Increased rate of occurrence of serious suspected adverse reactions

The sponsor must report any clinically important increase in the rate of a serious suspected adverse reaction over that listed in the protocol or investigator brochure.

9.3 Submission of IND safety reports

The sponsor must submit each IND safety report in a narrative format or on Form FDA 3500A or in an electronic format that FDA can process, review, and archive. FDA will periodically issue guidance on how to provide the electronic submission (e.g., method of transmission, media, file formats, preparation and

organization of files). The sponsor may submit foreign suspected adverse reactions on a Council for International Organizations of Medical Sciences (CIOMS) I Form instead of a Form FDA 3500A. Reports of overall findings or pooled analyses from published and unpublished in vitro, animal, epidemiological, or clinical studies must be submitted in a narrative format. Each notification to FDA must bear prominent identification of its contents, i.e., "IND Safety Report," and must be transmitted to the review division in the Center for Drug Evaluation and Research or in the Center for Biologics Evaluation and Research that has responsibility for review of the IND. Upon request from FDA, the sponsor must submit to FDA any additional data or information that the agency deems necessary, as soon as possible, but in no case later than 15 calendar days after receiving the request.

9.3.1 Unexpected fatal or life-threatening suspected adverse reaction reports

The sponsor must also notify FDA of any unexpected fatal or life-threatening suspected adverse reaction as soon as possible but in no case later than 7 calendar days after the sponsor's initial receipt of the information.

9.3.2 Reporting format or frequency

FDA may require a sponsor to submit IND safety reports in a format or at a frequency different than that required under this paragraph. The sponsor may also propose and adopt a different reporting format or frequency if the change is agreed to in advance by the director of the FDA review division that has responsibility for review of the IND.

9.3.3 Investigations of marketed drugs

A sponsor of a clinical study of a drug marketed and/or approved in the United States that is conducted under an IND is required to submit IND safety reports for suspected adverse reactions that are observed in the clinical study, at domestic or foreign study sites. The sponsor must also submit safety information from the clinical study as prescribed by the post marketing safety reporting requirements.

9.3.4 Reporting study endpoints

Study endpoints (e.g., mortality or major morbidity) must be reported to FDA by the sponsor as described in the protocol and ordinarily would not be reported under Section 1.7 third bullet of this section. However, if a serious and unexpected adverse event occurs for which there is evidence suggesting a causal relationship between a study drug and the event (e.g., death from anaphylaxis), such event must be reported as a serious and unexpected suspected adverse reaction even if it is a component of the study endpoint (e.g., all-cause mortality).

9.4 Follow-up

The sponsor must promptly investigate all safety information it receives.

Relevant follow-up information to an IND safety report must be submitted as soon as the information is available and must be identified as such, eg., "Follow-up IND Safety Report."

If the results of a sponsor's investigation show that an adverse event not initially determined to be reportable under IND safety reporting guidelines is, in fact, so reportable, the sponsor must report such suspected adverse reaction in an IND safety report as soon as possible, but in no case later than 15 calendar days after such determination is made.

9.5 Disclaimer

A safety report or other information submitted by a sponsor under this part (and any release by FDA of that report or information) does not necessarily reflect a conclusion by the sponsor or FDA that the report or information constitutes an admission that the drug caused or contributed to an adverse event. A sponsor need not admit, and may deny, that the report or information submitted by the sponsor constitutes an admission that the drug caused or contributed to an adverse event.

9.6 Reporting Adverse Events to the responsible IRB

In accordance with applicable policies of the University of Pittsburgh Institutional Review Board (IRB), the Sponsor-Investigator will report, to the IRB, any observed or volunteered adverse event that is determined to be 1) associated with the investigational drug or study treatment(s); 2) serious; and 3) unexpected. Adverse event reports will be submitted to the IRB in accordance with the respective IRB procedures.

Applicable adverse events will be reported to the IRB as soon as possible and, in no event, later than 10 calendar days following the sponsor-investigator's receipt of the respective information. Adverse events which are 1) possibly, probably or definitely attributed to the investigational drug(s) or study treatment(s); 2) fatal or life-threatening; and 3) unexpected, will be reported to the IRB within 24 hours of the Sponsor-Investigator's receipt of the respective information.

Follow-up information to a reported adverse event will be submitted to the IRB as soon as the relevant information is available. If the results of the Sponsor-Investigator's follow-up investigation show that an adverse event that was initially determined to not require reporting to the IRB does, in fact, meet the requirements for reporting; the Sponsor-Investigator will report the adverse event to the IRB as soon as possible, but in no event later than 10 calendar days, after the determination was made.

9.7 Other Safety Considerations

Any significant worsening of condition noted during interim or final physical examinations, electrocardiograms, radiologic exams, or any other assessment required or not required by protocol should be recorded as a nonserious or serious AE, as appropriate, and reported accordingly.

10.0 Data Safety Monitoring Plan

10.1 Study Oversight

Investigator/Sub-investigators, regulatory, CRS management, clinical research coordinators, clinical research associates, data managers, and clinic staff meet regularly in disease center Data Safety Monitoring Boards (DSMB) to review and discuss study data to include, but not limited to, the following:

- serious adverse events

- subject safety issues
- recruitment issues
- accrual
- protocol deviations
- unanticipated problems
- breaches of confidentiality

Minutes from the disease center DSMB meetings are made available to those who are unable to attend in person.

All toxicities encountered during the study will be evaluated on an ongoing basis according to the NCI Common Toxicity Criteria Version 5.0. All study treatment associated adverse events that are serious, at least possibly related to study drugs, and unexpected will be reported to the IRB. Any modifications necessary to ensure subject safety and decisions to continue or close the trial to accrual are also to be discussed during DSMB meetings. If any literature becomes available which changes the risk/benefit ratio or suggests that conducting the trial is no longer ethical, the IRB will be notified in the form of an Unanticipated Problem submission, and the study may be terminated.

All study data reviewed and discussed during DSMB meetings will be kept confidential. Any breach in subject confidentiality will be reported to the IRB in the form of an Unanticipated Problem submission. The summaries of these meetings are forwarded to the UPMC Hillman Cancer Center DSMC which also meets monthly following a designated format.

For all research protocols, there will be a commitment to comply with the IRB's policies for reporting unanticipated problems involving risk to subjects or others (including adverse events). DSMC progress reports, to include a summary of all serious adverse events and modifications, and approval will be submitted to the IRB at the time of renewal.

Protocols with subjects in long-term (survival) follow-up or protocols in data analysis only, will be reviewed bi-annually.

Both the UPMC Hillman Cancer Center DSMC as well as the individual disease center DSMB have the authority to suspend accrual or further investigate treatment on any trial based on information discussed at these meetings.

All records related to this research study will be stored in a locked environment. Only the researchers affiliated with the research study and their staff will have access to the research records.

10.2 Data Handling and Record Keeping

A Case Report Form (CRF) will be completed for each subject enrolled into the clinical study. Source Data are the clinical findings and observations, laboratory and test data, and other information contained in Source Documents. Source Documents are the original records including, but not limited to, hospital medical records, physician or office charts, physician or nursing notes, subject diaries or evaluation

checklists, pharmacy dispensing records, recorded data from automated instruments, x-rays, etc. When applicable, information recorded on the CRF shall match the Source Data recorded on the Source Documents.

11.0 Management of Adverse Events with Duvelisib

Management of adverse events often depends on clinical context. From prior experience, suggestions regarding duvelisib toxicities are below per product insert and investigator's brochure. Please refer to section 7.6 for information on managing AEs with nivolumab and duvelisib. Please also refer to published guidelines from ASCO for management of immune-related adverse events²³.

11.1 Infections

Duvelisib carries a black box warning regarding infection risk, most often URI and pneumonia. The median time to infection was 3 months, with the majority occurring prior to 6 months. For any grade 3 or higher infection, duvelisib must be held. For patients with suspected PJP, duvelisib should be held and permanently discontinued if PJP is confirmed. PJP prophylaxis is required for all patients and should continue until CD4+ T cell count is > 200 cells/ μ L or for 14 days after last dose of duvelisib. For patients with CMV reactivation or infection, drug should be held until resolved. If resumed, patients should be monitored at least monthly for reactivation and prophylaxis should be considered. For other infections, recommended dose reductions are listed in Table 7.5.

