4.4 Subject Withdrawal or Termination

4.4.1 Termination of Study Participation

In the absence of treatment delays due to adverse event(s), treatment may continue until one of the following criteria applies:

- Disease Progression
- Intercurrent illness that prevents further administration of treatment
- Unacceptable adverse event(s)
- Patient decides to withdraw from the study
- General or specific changes in the patient's condition render the patient unacceptable for further treatment in the judgement of the investigator
- Patient non-compliance
- Pregnancy
 - All WCBP will be instructed to contact the investigator immediately if they suspect pregnancy at any time during study participation
 - The investigator must immediately notify the IRB in the event of a confirmed pregnancy in a patient participating in the study
- Termination of the study by sponsor
- Loss of access to one or both investigational agents
- The maximum planned duration treatment of 12 months has been completed.

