4.4.1 Duration of Follow Up and Retreatment

The period of acute toxicity and DLT evaluation is 28 days. Beyond that, AEs that arise while on treatment and within 4 weeks (+ 2 weeks) after discontinuation of treatment will be considered late toxicities

Patients will be evaluated by the treating physician after trial discontinuation, regardless of reason for discontinuation. Patients will be seen for an additional visit 4 weeks (+ 2 weeks) after study discontinuation to evaluate for additional adverse events and will continue to be followed until all adverse events have resolved or stabilized. The investigator and treating physician are responsible to ensure, within reason, that the patients receive appropriate treatment for their malignancy after trial discontinuation. Patients may be contacted for survival follow-up for up to 5 years. Survival follow-up will be performed approximately every 3 months. Patients terminated from the trial for adverse events will be followed until resolution or stabilization of the adverse event. Patients will have regular lab work and need documentation of CD4 T-cell subset >200 cells/ μ L prior to stopping PJP prophylaxis. We anticipate 3 years of data collection to determine duration of response.

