6.4 Laboratory Evaluations

Blood sampling will be performed with the laboratory tests below at each visit, with exceptions noted below:

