6.4.1 Table: Clinical Laboratory Tests

Category	Tests
Hematology	Hemoglobin, hematocrit, platelet count, WBC with differential. CD4+ T cell subsets will be checked at screening and at study discontinuation and monthly until CD4+ threshold is reached.

Serum chemistries	Sodium, potassium, chloride, Co2, BUN, creatinine, calcium, glucose, LDH
Liver function tests	SGOT/AST, SGPT/ALT, total Bilirubin, alkaline phosphatase, albumin
Endocrine tests	TSH with free T4, T3 as applicable; Cortisol and ACTH if clinician concerned for hypophysitis
Infectious disease	HIV, Hepatitis C Ab, Hepatitis B Surface Ag, Hepatitis B Surface Ab, Hepatitis B Core Ab on screening only
Pregnancy test	Serum or urine β hCG testing on screening only

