	Mild/moderate diarrhea (Grade 1-2, up to 6 stools per day over baseline) and unresponsive to antidiarrheal agents	
Duvelisib
 
 - Withhold duvelisib until resolved - Initiate supportive therapy with systemic steroids - Monitor at least weekly until resolved - Resume at a reduced dose - Gastroenterology consultation, recommend endoscopy and biopsy 
Nivolumab
 
 - Withhold nivolumab until resolved - Resume at same dose - Support with systemic steroids, gastroenterology consultation, recommend endoscopy and biopsy
	Abdominal pain, stool with mucus or blood, change in bowel habits, peritoneal signs, OR Severe diarrhea (Grade 3, >6 stools per day over baseline)	
Duvelisib
 
 - Withhold duvelisib until resolved - Initiate supportive therapy with enteric acting steroids (e.g., budesonide) or systemic steroids - Monitor at least weekly until resolved - Resume at a reduced dose

Toxicity	Adverse Reaction Grade	Recommended Management
		
 - For recurrent Grade 3 diarrhea or recurrent colitis of any grade, discontinue duvelisib 
Nivolumab
 
 - Withhold nivolumab until resolved - Resume at same dose - Systemic steroids, gastroenterology consultation and biopsy - If no improvement in 3-5 days, consider addition of infliximab
	Life-threatening, grade 4	
Duvelisib
 
 - Discontinue duvelisib 
Nivolumab
 
 - Permanently discontinue nivolumab - Systemic steroids, gastroenterology consultation and biopsy - If no improvement in 3-5 days, consider addition of infliximab
Cutaneous reactions	Grade 1	
Duvelisib
 
 - No change in dose - Initiate supportive care with emollients, antihistamines (for pruritus), or topical steroids - Monitor closely 
Nivolumab
 
 - Continue nivolumab - Support with topical emollients and/or mild-moderate potency topical corticosteroids
	Grade 2	
Duvelisib
 
 - Consider holding duvelisib, restart at same dose - Initiate supportive care with emollients, antihistamines (for pruritus), or topical steroids - Monitor closely 
Nivolumab
 
 - Consider holding nivolumab until resolved - Resume at same dose once improved to grade 1

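### Section 11.1 lets PJP prophylaxis stop 14 days after the last duvelisib dose whatever the CD4 count, while 4.4.1 (Duration of Follow Up and Retreatment) requires a documented CD4 above 200 first

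*Combined protocol and SAP*

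**What the plan says.** Three places bear on when PJP prophylaxis may end.

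- **Section 11.1 (Infections)** makes prophylaxis mandatory for everyone and says it should continue until CD4+ exceeds 200 cells/µL "or for 14 days after last dose of duvelisib". Nothing such as 'and', 'at least' or 'whichever is later' links the two conditions.
- **Section 4.4.1, Duration of Follow Up and Retreatment** (the second of two sections with that number) says: "Patients will have regular lab work and need documentation of CD4 T-cell subset" above 200 cells/µL "prior to stopping PJP prophylaxis". It offers no alternative based on elapsed time.
- **Section 6.4 and Table 6.4.1** set the laboratory schedule. The general rule is "Blood sampling will be performed with the laboratory tests below at each visit, with exceptions noted below". CD4 is one of the exceptions: "CD4+ T cell subsets will be checked at screening and at study discontinuation and monthly until CD4+ threshold is reached".

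Section 6.8 covers only the start of prophylaxis. No section says which stopping rule prevails.

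**The concern.** A clinician looking for the stopping rule is likely to turn to the infections section, 11.1. Read alone, it allows prophylaxis to end on day 14 after the last capsule in a patient whose CD4 is 200 or lower, or has not been measured since screening. Section 4.4.1 would keep that patient on prophylaxis. The same section 11.1 notes duvelisib's boxed warning for infection, so the measure that could be withdrawn too early is one the protocol itself treats as essential.

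The laboratory schedule does not remove the problem. The 14-day clock runs from the last duvelisib dose, whereas the CD4 tests in Table 6.4.1 hang on screening and study discontinuation.

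**Working it through.** The plan gives no figure to reproduce. The check is a comparison of the two rules, followed by a timing calculation.

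**Step 1: the two rules side by side.** Take a patient who has been off duvelisib for at least 14 days.

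| CD4 status | 11.1 | 4.4.1 (Follow Up) |
|---|---|---|
| Documented above 200 | may stop | may stop |
| Documented 200 or lower | may stop | may not stop |
| Undocumented | may stop | may not stop |

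The rules disagree in the last two rows. This result needs no assumption about scheduling.

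**Step 2: when CD4 is next measured.** Inputs and assumptions:

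- Day 0 is the last duvelisib dose, so the stop allowed by 11.1 falls on day 14.
- G is the number of days from the last duvelisib dose to study discontinuation. I take study discontinuation to mean the end of all study treatment; the protocol does not define it for this purpose.
- Monthly is taken as 28 to 31 days.
- Table 6.4.1 is read as testing at screening, then at study discontinuation, then monthly until the threshold is met.

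*Same-day stop (G = 0).* CD4 is tested on day 0. If it is 200 or lower, the retest falls on day 28 to 31. The gap after the permitted stop is 28 − 14 = 14 days to 31 − 14 = 17 days. The follow-up visit in 4.4.1, at 4 weeks (+ 2 weeks) after study discontinuation, also falls no earlier than day 28.

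*Duvelisib stops first (G > 14).* The next scheduled CD4 is on day G, so no test is scheduled between screening and day 14. The first one comes G − 14 days after the permitted stop: for example 28 − 14 = 14 days, or 84 − 14 = 70 days. These values of G are arbitrary and only show how the gap grows.

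**Step 3: can duvelisib stop before study participation?** It can. Section 4.4.2 keeps patients who ask to stop study treatment on the study for follow-up. In the severe-diarrhea row of Table 7.6 the duvelisib entry reads "For recurrent Grade 3 diarrhea or recurrent colitis of any grade, discontinue duvelisib", while the nivolumab entry in the same row begins "Withhold nivolumab until resolved" and then resumes the same dose. That row gives no separate nivolumab instruction for a recurrence, so it shows that the sequence is possible and no more.

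**Step 4: does the sample timing matter?** Neither 11.1 nor 4.4.1 says when the qualifying CD4 must be drawn. Table 6.4.1 includes a screening test, so a screening value above 200 would literally count as documentation while the patient is still taking duvelisib. A repair has to close this as well.

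**The case against.** The strongest reply is that a careful site meets no dilemma. Continuing prophylaxis satisfies both sections, section 11.0 introduces its contents as suggestions, and Table 6.4.1's monthly testing until the threshold is reached fits the CD4 rule. The authors may also have meant 14 days as a minimum. The first point stands: the fault is that 11.1 permits a stop, not that it demands one. The others do not settle the matter. The sentence in 11.1 itself makes prophylaxis compulsory, and a minimum is not what it says. Section 15.0 expects melanoma patients to be less immunosuppressed than those with hematologic malignancies, which may make low counts less common but does not reconcile the rules.

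A second reply concerns scheduling. Unacceptable adverse events are listed in 4.4.1 (Termination of Study Participation) as ending treatment, so many duvelisib stops may coincide with study discontinuation and bring a CD4 test on that day. Also, if monthly testing is read as running throughout treatment, the next test is at most about 28 to 31 days away. Both points narrow the scheduling gap. Neither removes the conflict, which is already present at G = 0 with a low count.

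A reader might go further and infer that patients with colitis would routinely spend many months on nivolumab with no CD4 test, by setting the 4-month median onset in 11.2 against the end point "The maximum planned duration treatment of 12 months has been completed". The documents do not support that. The 4 months is time to first onset, whereas permanent discontinuation in that row of Table 7.6 requires a recurrence, which comes later. Nothing shows that nivolumab would continue to the 12-month limit in such a patient.

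**Conclusion.** The contradiction is real and in current text: 11.1 permits a stop that 4.4.1 (Duration of Follow Up and Retreatment) forbids. It is confined to patients at least 14 days off duvelisib whose CD4 is 200 or lower or undocumented, and the documents do not allow their number to be estimated.

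The 14-to-17-day delay to retest in the same-day case assumes only that monthly means 28 to 31 days and that study discontinuation is the end of study treatment. The case in which no test is scheduled by day 14 is possible under Table 6.4.1, but its frequency is unknown, and I attach no typical length to it.

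The point should be corrected because it concerns a mandatory safety measure and the repair is cheap. It does not touch the trial's inference.

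**What to change.** Two small edits, made together:

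1. **Section 11.1.** Replace the either/or rule with: *All patients take PJP prophylaxis throughout duvelisib treatment; it must not be stopped until CD4 >200 cells/µL is documented on a sample taken after the last duvelisib dose (see 4.4.1, Duration of Follow Up and Retreatment).*
2. **Table 6.4.1.** Schedule CD4 at permanent duvelisib discontinuation, then monthly until above 200, as well as at study discontinuation.

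Deleting the 14-day clause alone would not be enough: a screening value could still qualify, and the test schedule would remain unconnected to the last dose.

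The cost is a short amendment, somewhat longer prophylaxis in patients whose CD4 recovers slowly (which 4.4.1 already requires), and possibly one earlier CD4 blood test. The requirement for a post-dose sample is a clarification that no section currently states, so the sponsor would need to adopt it knowingly.
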